14.2. Monitoring Adverse Events

At each visit, subjects will be queried regarding any AEs that have occurred since the last visit. Subjects will be asked to volunteer information concerning AEs with a non-leading question such as, “How do you feel?” Study site personnel will then record all pertinent information in the source documents and the eCRF. The study drug compliance record should also be reviewed to detect potential overdoses (intentional/unintentional).

14.3. Relationship to Study Drug

The degree of “relatedness” of the AE to the study medication must be described using the following scale:

- **Not related** indicates that the AE is definitely not related to the study medication.
- **Unlikely related** indicates that there are other, more likely causes and study medication is not suspected as a cause.
- **Possibly related** indicates that a direct cause and effect relationship between study medication and the AE has not been demonstrated, but there is evidence to suggest there is a reasonable possibility that the event was caused by the study medication.
- **Probably related** indicates that there is evidence suggesting a direct cause and effect relationship between the AE and the study medication.

It is the Sponsor’s policy to consider “Probably related” and “Possibly related” causality assessments as positive causality. “Not related” and “Unlikely related” causality assessments are considered as negative causality.

Assessments will be recorded on the eCRF and must indicate clearly the relationship being assessed. For example, an AE that appears during a placebo run-in phase would be assessed with respect to the placebo treatment received and/or study procedures conducted during this phase. If the AE continued into an active treatment phase, the relationship would be assessed for the active treatment phase only if the AE worsened.

14.4. Intensity Assessment

The intensity (or severity) of AEs is characterized as mild, moderate, or severe:

- **Mild** AEs are usually transient, requiring no special treatment, and do not interfere with the subject's daily activities.
- **Moderate** AEs introduce a low level of inconvenience or concern to the subject and may interfere with daily activities, but are usually ameliorated by simple therapeutic measures.
- **Severe** AEs interrupt a subject's usual daily activity and typically require systemic drug therapy or other treatment.

When the intensity category of an AE changes, the greatest intensity during that continuous episode should be recorded.

14.5. Reporting Adverse Events and Serious Adverse Events

14.5.1. Reporting Adverse Events

Throughout the study, AEs will be documented on the source document and on the appropriate page of the eCRF whether or not considered treatment-related. This includes any new signs, symptoms, injury or illness, including increased severity of previously existing signs, symptoms, injury, or illness. Conditions existing prior to screening will be recorded as part of the subject's medical history. The Investigator is responsible for assessing the relationship of AEs to the study medication; relationship will be classified as not related, unlikely related, possibly related, or probably related.

All AEs will be collected by the Investigator from the time of signing the informed consent through 28 days after the last dose of study medication; this includes any AEs that are ongoing at the time of completion/termination of the study. All ongoing AEs must be followed until resolution or for 14 days after the subject's last study visit, whichever comes first.

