
Investigational product, dosage, and mode of administration: Investigational product is CCH. A single dose of 3.36 mg of CCH will be administered as 12 subcutaneous injections (CCH 0.84 mg) per quadrant concurrently in 4 quadrants for a total of 48 injections. A quadrant is defined as one of the following: left buttock, right buttock, left posterolateral thigh, or right posterolateral thigh.
 
The study drug (CCH) will be injected subcutaneously while subject is in a prone position using a syringe with a 30-gauge ½-inch needle. Each injection site will receive a single skin injection of study drug administered as three 0.1-mL aliquots (for a total injection volume of 0.3 mL per injection; an injection volume of 3.6 mL per quadrant and a total injection volume of 14.4 mL).

Duration of study: 43 days (includes screening phase)
 
Screening Phase: Up to 21 days
 
Dosing Phase: Subjects will be admitted to the research unit on the afternoon of Day –1. Dosing will occur on Study Day 1. Subjects will remain in the research unit for collection of the PK samples out to 24 hours post dose. They will then be discharged after the last sample is collected on Study Day 2.
 
Follow up: Subjects will return to the study unit on Day 3, 8, and 22 for outpatient follow-up PK, immunogenicity, and safety assessments. The last scheduled outpatient visit to the clinic for assessments is on Study Day 22.

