11.3. Subject Discontinuation Criteria

Subjects who have signed the informed consent may be discontinued or withdrawn from study treatment or the entire study at any time at their own request, or any time at the discretion of the investigator for the following reasons:

- An AE
- A protocol violation (reason must be specified, for example: lack of compliance with the protocol requires visits and assessments, use of a prohibited concomitant medication, failure to meet inclusion/exclusion criteria after study entry, etc)
- Withdrawal by subject (reason must be specified)
- The subject was “lost to follow-up”
- Other reasons (reason must be specified, for example: the subject moved, pregnancy, Investigator decision, Sponsor decision to terminate trial, etc)

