6.2. Derived Variables

Refer to [Table 11](#) for the listing of the derived variables and their definitions for study parameters.

Table 11: Derived Variables and Definition

Variable	Definition
Height (cm)	If height is recorded in inches, then height is equal to the recorded value multiplied by 2.54 and then rounded to 1 decimal point.
Weight (kg)	If weight is recorded in pounds, then weight is equal to the recorded value multiplied by 0.454 and then rounded to 1 decimal point.
Body Mass Index (BMI)	BMI will be computed using height and body weight measured at screening as, $BMI \text{ (kg/m}^2\text{)} = \text{Weight (kg)} / \text{Height (m)}^2$
Relative Day	The day of first injection of study drug will be considered as relative day 1
Study Day (for assessment on or after the Day 1)	Study Day will be computed as, Date of Assessment – Date of Day 1 + 1
Study Day (for assessment before Day 1)	Study Day will be computed as, Date of Assessment – Date of Day 1
Baseline	Baseline is defined as the last non-missing measurement/assessment prior to the first dose of study drug. For vital signs, the baseline will be the Day 1 pre-dose values. For clinical laboratories this could be the screening value, or it could be an unscheduled lab, if the unscheduled lab is the closest value preceding the first injection.
Change from Baseline	Change from baseline will be derived as, post-baseline visit/time point value – the baseline value.
Last Date in Study	End date of last visit where subject was seen by investigator. If subject was lost to follow-up, then last date of contact. If the subject had contact with the site after the final visit (eg, to follow-up on an AE), the last visit date will still be used as last date in the study.
Time in Study	Last date in study – Date of first injection + 1
Age at EFP Symptom Onset	Date of EFP symptoms reported – Date of Birth/365.25. See section 6.3.1.3 for handling of partial or unknown EFP symptom onset dates.
Time since last EFP treatment	Date of most recent EFP treatment – Date of informed consent)/365.25. See section 6.3.1.3 for handling of partial or unknown EFP treatment dates.
Baseline CR-PCSS Score	Investigator baseline CR-PCSS scores for each quadrant will be based on the investigator's CR-PCSS evaluation done at the Screening visit.

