7.9.2. Adverse Events

All AE summary tables will include only TEAEs, unless otherwise specified.

AEs will be summarized by SOC and PT. A subject will only be counted once per SOC and PT.

For AEs by severity grade (mild, moderate, severe), if a subject has multiple events occurring in the same SOC or same PT, then the event with the maximum intensity (ie, severe) will be counted.

For AEs by relationship to study drug, if a subject has multiple events occurring in the same SOC or same PT, the event with the highest association (ie, related) to study drug will be summarized.

AEs will be presented in decreasing order of the incidences at SOC level and within each SOC, in decreasing order of the incidences at the PT level.

An overall summary of AE and AE related to study drug will be presented and will include:

- Total number of TEAEs reported
- Total number of TEAEs reported by severity
- Total number of AEs of special interest
- Subjects with any TEAE
- Subjects with any AE of special interest
- Subjects with any serious TEAE
- Subjects with any severe TEAE
- Subjects with no severe TEAEs, but at least one moderate TEAE
- Subjects with no severe TEAEs, but at least one mild TEAE
- Subjects with any TEAEs leading to drug interruption/withdrawn
- Subjects with any TEAEs leading to study discontinuation
- Subjects with any TEAEs resulting in death

Statistical Analysis Plan (SAP) Module 1 – Study EN3835-103

The following summary tables will be presented by SOC and PT:

- All TEAEs
- TEAEs by Severity
- All non-study drug related TEAEs
- All study drug related TEAEs
- Study drug related TEAEs by severity
- Serious TEAEs
- Duration of study drug related TEAEs (<14 days, 14 – 21 days and >21 days)
- AEs of Special Interest

Serious and most common non-serious TEAE by order of frequency (Most frequent, 2nd most frequent and 3rd most frequent) will be summarized by PT. Most common non-serious AEs are any PT that at least 5% of the subjects reported at least once.

The following listings will be presented by patient:

- All AEs
- Serious AEs
- AEs of special interest
- AEs resulting in drug interruption/withdrawn
- AEs resulting in study discontinuation
- AEs resulting in deaths

Refer to [Table 11](#) for computation of duration of AE.

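### Required follow-up of an ongoing non-serious AE can end before AE collection ends when a subject's last visit is on or before Day 14

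*Protocol*

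**What the plan says.** Protocol Section 14.5.1 sets two limits in adjacent sentences.

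- **Collection.** AEs are collected from consent "through 28 days after the last dose of study medication", and "this includes any AEs that are ongoing at the time of completion/termination of the study".
- **Follow-up.** "All ongoing AEs must be followed until resolution or for 14 days after the subject's last study visit, whichever comes first".

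Other passages bear on how these limits work.

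- Section 14.5.2 gives SAEs their own rule, with no 14-day limit: they are followed until they resolve or stabilise, or until follow-up is no longer possible.
- Section 11.3.2 encourages subjects who leave the study to complete the end-of-study procedures. SAP Section 6.3 asks them to do so at an early termination visit. Neither fixes a day for that visit.
- Footnote j of the protocol's schedule of events (Section 5) and footnote j of SAP Table 1 both end AE capture at Day 22, not Day 29.
- SAP Section 7.9.2 plans a table of "Duration of study drug related TEAEs" in three classes: <14, 14–21 and >21 days.

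**The concern.** Assessing safety is a primary objective, and how long local reactions last is one of the planned safety summaries. The two limits in Section 14.5.1 run from different starting points. For a completer, follow-up outlasts collection. For a subject who leaves early enough, the order reverses: new events must still be collected from her, but a reaction already on record no longer has to be followed.

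At stake is whether the outcome and duration of a persistent non-serious reaction are known for subjects who leave early. An AE is one of the listed reasons for leaving (Section 11.3), so the shorter requirement may fall on subjects whose reactions are of interest.

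**Working it through.** **Inputs**

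- Day of the only dose: "Dosing will occur on Study Day 1" (Protocol synopsis).
- Day scale: "Study Day will be computed as, Date of Assessment – Date of Day 1 + 1" (SAP Section 6.2), so there is no Day 0.
- First scheduled departure from the unit: "They will then be discharged after the last sample is collected on Study Day 2" (Protocol synopsis). Outpatient visits are on Days 3, 8 and 22.
- Collection limit: dose + 28 days. Follow-up limit: last visit + 14 days (both Protocol Section 14.5.1).
- AE duration: end date − start date + 1 (SAP Table 11).

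**Check of the day scale.** The schedule places 24, 48, 168 and 504 hours after dosing at Days 2, 3, 8 and 22. Day 1 plus 1, 2, 7 and 21 days gives the same days.

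**Formulas**

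- Collection ends on Day 1 + 28 = Day 29.
- Required follow-up ends on Day V + 14, where V is the day of the last visit.
- Shortfall = 29 − (V + 14) = 15 − V. It is positive only if V ≤ 14.
- Longest duration of a Day 1 reaction within required follow-up = (V + 14) − 1 + 1 = V + 14 days. It exceeds 21 only if V ≥ 8.

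**Results**

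| Last visit (V) | Required follow-up ends | Days short of Day 29 | Days short of Day 22 | Longest duration of a Day 1 reaction within required follow-up |
|---|---|---|---|---|
| Day 1 | Day 15 | 14 | 7 | 15 days |
| Day 2 | Day 16 | 13 | 6 | 16 days |
| Day 3 | Day 17 | 12 | 5 | 17 days |
| Day 7 | Day 21 | 8 | 1 | 21 days |
| Day 8 | Day 22 | 7 | 0 | 22 days |
| Day 14 | Day 28 | 1 | none | 28 days |
| Day 15 | Day 29 | 0 | none | 29 days |
| Day 22 (completer) | Day 36 | none | none | 36 days |

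Days 1, 7, 14 and 15 are not scheduled outpatient visits. They stand for a subject last seen on the dosing day, or for an early termination visit on that day.

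The Day 22 column shows that settling the conflict over the end of collection would not by itself close the gap. If Day 22 were kept, subjects last seen on Day 2 or Day 3 would still fall 6 or 5 days short.

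**The case against.** The strongest reply is that this is an unclear junction and not a contradiction. Collecting AEs and following a known AE are different tasks, and the collection sentence expressly takes in events ongoing at termination. An early termination visit becomes the last study visit and restarts the 14 days. If it falls on Day 15 or later, nothing is lost. The protocol also reports that TEAEs in earlier studies were mostly transient (Section 8.1.1), and that most AEs resolved before the next treatment at 21-day intervals (Section 10.2). All of this stands, and it limits the point to subjects last seen by Day 14. It does not remove the point, because the end-of-study visit is only encouraged or requested, has no set day, and may be held on the day she leaves.

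A reader might draw stronger conclusions that the documents do not support.

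- **That a persistent reaction in an early leaver can never be recorded as lasting more than 21 days.** The text sets the minimum follow-up and does not bar later recording.
- **That the duration table will understate persistence.** This is not shown. An unresolved AE has no end date, and the SAP has no rule for placing it in a duration class. That omission also affects completers.
- **That two of the 12 subjects is an upper limit on those affected.** Ten completers is a stated aim and not a cap on losses. An early leaver is affected only if she also has an unresolved non-serious AE and no visit after Day 14.
- **That Section 11.3 needs rewriting**, because subjects may be "withdrawn from study treatment or the entire study at any time at their own request, or any time at the discretion of the investigator". Whether an investigator may withdraw a subject for an AE is a separate question, close to clinical management. Repairing Section 14.5.1 does not depend on it. Section 11.3.1 already encourages subjects withdrawn from treatment to complete the other procedures, and Section 11.3.2 keeps collection of AE information even when consent is withdrawn.

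**Conclusion.** The point holds as a narrow gap in required follow-up. For a last visit on or before Day 14, required follow-up of an ongoing non-serious AE ends before Day 29. The shortfall is 13, 12 or 7 days for a last visit at the scheduled Day 2, 3 or 8 visit. For a last visit by Day 7, a Day 1 reaction cannot reach the >21-day class within required follow-up.

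This rests on three assumptions: no visit takes place after the stated day, the single dose is on Day 1, and the collection limit in Section 14.5.1 stands. If Day 22 applies instead, the gap is confined to a last visit by Day 7 and is at most 6 days for subjects discharged on Day 2 or later.

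The documents do not give the number of subjects affected. It is likely small, given 12 enrolled and an aim of at least 10 completers. The case for a change is that the repair is cheap and serves a primary objective, not that a bias has been demonstrated.

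**What to change.** 1. Reconcile the end of AE collection: Day 29 in Protocol Section 14.5.1 against Day 22 in footnote j of the protocol schedule and of SAP Table 1. This review does not say which is right.
2. Then reword the follow-up limit in Section 14.5.1 so that ongoing AEs are followed until resolution or until the later of (a) 14 days after the last study visit and (b) the reconciled end of AE collection, which is 28 days after dosing if Section 14.5.1 stands.

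With this wording, required follow-up of an unresolved AE runs at least to the end of collection for every early leaver. A Day 1 reaction could then be followed for at least 29 − 1 + 1 = 29 days, or 22 − 1 + 1 = 22 days if Day 22 is chosen. Either allows the >21-day class to be reached. Subjects who are lost to follow-up gain nothing from the change, and it does not settle how the SAP should class an AE still unresolved at the cut-off.

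The cost is one reworded sentence, the matching correction of the collection date, and one or two extra follow-up contacts per early leaver. No further subjects or study procedures are needed.

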14.5.2. Reporting Serious Adverse Events

Any SAE, including death resulting from any cause, which occurs to any subject participating in this study must be reported via email to [REDACTED] the Investigator using the Endo Serious Adverse Event (SAE)/Reportable Event Form within 24 hours of first becoming aware of the SAE. SAEs will be collected by the Investigator from the time of signing the informed consent through 28 days after the last dose of study drug. Any SAE that is felt by the Investigator to be related to the study medication must be reported regardless of the amount of time since the last dose received. Follow-up information collected for any initial report of an SAE must also be reported to the Sponsor within 24 hours of receipt by the Investigator.

All SAEs will be followed until resolution, stabilization of condition, or until follow-up is no longer possible.

In the event discussion is necessary regarding treatment of a subject, call the Medical Monitor (see contact information in Section 3).

All SAEs should be sent via the email address, or faxed to the fax number, provided in Section 3.

The Sponsor will determine whether the SAE must be reported within 7 or 15 days to regulatory authorities in compliance with local and regional law. If so, the Sponsor (or the Sponsor's representative) will report the event to the appropriate regulatory authorities. The Investigator will report SAEs to the IRB per their IRB policy.

14.5.2.1. Follow-up Procedures for Serious Adverse Events

To fully understand the nature of any SAE, obtaining follow-up information is important. Whenever possible, relevant medical records such as discharge summaries, medical consultations, and the like should be obtained. In the event of death, regardless of cause, all attempts should be made to obtain the death certificate and an autopsy report. These records should be reviewed in detail, and the Investigator should comment on any event, lab abnormality, or any other finding, noting whether it should be considered a serious or non-serious AE, or whether it should be considered as part of the subject's history. In addition, all events or other findings determined to be SAEs should be identified on the follow-up SAE form and the Investigator should consider whether the event is related or not related to study drug. All events determined to be non-serious should be reported on the eCRF.

14.6. Special Reporting Situations

14.6.1. Adverse Events of Special Interest

[REDACTED]

will be reported as an AE in the eCRF. All AEs will be evaluated for seriousness and severity. If any of these events meet the criteria for an SAE, they will also be reported as such using the procedure outlined in Section 14.5.2.

14.6.2. Overdose/Misuse/Abuse

14.6.2.1. Overdose

Study drug overdose is any accidental or intentional use of study drug in an amount higher than the dose indicated by the protocol for that subject. Study drug compliance (see Section 12.6) should be reviewed to detect potential instances of overdose (intentional or accidental).

Any study drug overdose during the study should be noted on the study medication eCRF.

An overdose is not an AE per se, however all AEs associated with an overdose should both be entered on the Adverse Event eCRF and reported using the procedures detailed in Section 14.5.2, even if the events do not meet seriousness criteria. If the AE associated with an overdose does not meet seriousness criteria, it must still be reported using the Serious Adverse Event (SAE)/

Reportable Event Form and in an expedited manner, but should be noted as non-serious on the form and the Adverse Event eCRF.

14.6.3. Pregnancy

Any uncomplicated pregnancy that occurs in a subject during this clinical study will be **reported for tracking purposes only**. All subject pregnancies that are identified during or after this study, where the estimated date of conception is determined to have occurred during study drug dosing or within 22 days of the last dose of study medication need to be reported, followed to conclusion, and the outcome reported, even if the subject is discontinued from the study. The Investigator should report all pregnancies within 24 hours using the Pregnancy Form, and any pregnancy-associated SAE using the SAE report form, according to the usual timelines and directions for SAE reporting provided in Section 14.5.2. Monitoring of the pregnancy should continue until conclusion of the pregnancy; 1 or more Pregnancy Form(s) detailing progress, and a Two Month Follow-up Pregnancy Report Form detailing the outcome, should be submitted.

Pregnancy itself is not regarded as an AE unless there is suspicion that the investigational product under study may have interfered with the effectiveness of a contraceptive medication. Likewise, elective abortions without complications are not considered AEs. Any SAEs associated with pregnancy (eg, congenital abnormalities/birth defects/spontaneous miscarriages or any other serious events) must additionally be reported as such using the SAE report form. Spontaneous miscarriages should also be reported and handled as SAEs.

Subjects should be instructed to immediately notify the Investigator of any pregnancies.

Attempts to obtain the pregnancy follow-up and pregnancy outcome information detailed above are necessary even if a subject discontinues from the study because of pregnancy.

14.6.4. AEs/SAEs Experienced by Nonsubjects Exposed to Study Medication

Nonsubjects are persons who are not enrolled in the study but have been exposed to study medication, including instances of diversion of study medication. All such AEs/SAEs occurring in non-subjects from such exposure will be reported to the Endo Pharmacovigilance and Risk Management (PVRM) Department (when the non-subject agrees) on the Serious Adverse Event (SAE)/Reportable Event Form for serious adverse experiences regardless of whether the event is serious or not. Instructions for completing the form for events experienced by nonsubjects will be provided. SAEs occurring in nonsubjects exposed to study medication will be processed within the same SAE reporting timelines as described in Section 14.5.2. Additionally, the drug accountability source documentation at the site should reflect this occurrence.

